**Table 68: Percentage of Subjects Abstinent from Alcohol Weeks 3-6 – mITT Subjects**

Presented in same manner as Table 66

**Table 69: Percentage of Subjects Abstinent from Alcohol Weeks 3-6 – Full Model Logistic Regression (mITT)**

Presented in same manner as Table 67 *programming note: baseline PDA is a covariate for PSA outcome*

**Table 70: WHO 1-Level Decrease in Alcohol Consumption (mITT) – Weeks 3-6**

	ASP8062	Placebo	Total
	(N=xx)	(N=xx)	(N=xxx)
WHO 1-Level Decrease			
Yes	xx (xx.x%)	xx (xx.x%)	xx (xx.x%)
No	xx (xx.x%)	xx (xx.x%)	xx (xx.x%)

**Table 71: WHO 1-Level Decrease in Alcohol Consumption (mITT) – Full Model, Logistic Regression, Weeks 2-5**

									95% CI 	
Parameter		DF 	Estimate	Standard Error	Wald Chi-Square	Pr > Chi-Square	Cohen's h	OR 	Upper	Lower
Intercept		1	xx.XXX	xx.XXX	xx.XXX	0.xxx				
Treatment	Overall	X	xx.XXX	xx.XXX	xx.XXX	0.xxx				
Treatment 	ASP8062	X	xx.XXX	xx.XXX	xx.XXX	0.xxx	0.xxx	xx.XXX	xx.XXX	xx.XXX
Site	Overall	X	xx.XXX	xx.XXX	xx.XXX	0.xxx				
Site 	1	X	xx.XXX	xx.XXX	xx.XXX	0.xxx		xx.XXX	xx.XXX	xx.XXX
Site	2	X	xx.XXX	xx.XXX	xx.XXX	0.xxx		xx.XXX	xx.XXX	xx.XXX
Cov		X	xx.XXX	xx.XXX	xx.XXX	0.xxx		xx.XXX	xx.XXX	xx.XXX

 DF is degrees of freedom;  OR is odds ratio;  CI is confidence interval;  Comparison to placebo;

 Site 3 is reference for the OR

*Programming note: COV is baseline equivalent of dependent variable and any other covariate(s) which have not been specified at the time of writing of SAP*

**Table 72: WHO 2-Level Decrease in Alcohol Consumption (mITT) – Weeks 3-6**

Same as Table 70

**Table 73: WHO 2-Level Decrease in Alcohol Consumption (mITT) – Full Model, Logistic Regression, Weeks 3-6**

Same as Table 71

**Table 74: Percentage of Days Abstinent per Week (mITT) – Weeks 3-6**

Study Week	N	ASP8062			N	Placebo		
		Mean (SD  )	Median	(Min-Max)		Mean (SD)	Median	(Min-Max)
3	xx	xxx (xx)	xxx	(xx-xx)	xx	xxx (xx)	xxx	(xx-xx)
4	xx	xxx (xx)	xxx	(xx-xx)	xx	xxx (xx)	xxx	(xx-xx)
5	xx	xxx (xx)	xxx	(xx-xx)	xx	xxx (xx)	xxx	(xx-xx)
6	xx	xxx (xx)	xxx	(xx-xx)	xx	xxx (xx)	xxx	(xx-xx)
Overall	xx	xxx (xx)	xxx	(xx-xx)	xx	xxx (xx)	xxx	(xx-xx)

 SD is standard deviation

**Table 75: Percentage of Days Abstinent per Week (mITT) -- Full Model, Mixed Effects, Weeks 3-6**

**Type III Wald Tests**

Parameter	Num DF 	Den DF 	F Value	p-value
Arm	1	xxx	xxx.xx	0.xxx
Week	3	xxx	xxx.xx	0.xxx
Site	xx	xxx	xxx.xx	0.xxx
Cov	x	xxx	xxx.xx	0.xxx
Arm*Week	5	xxx	xxx.xx	0.xxx

 Numerator degrees of freedom;  Denominator degrees of freedom

*Programming note: Cov is the baseline equivalent of the dependent variable and any additional covariates included in the model.*

**Least Squares Means**

Arm	Week	Estimate	SE 	95% CI 		Difference	SE	p-value	Cohen's d	Model	
				Lower CI	Upper CI						
ASP8062	3	xx.xx	0.xxx	0.xxx	0.xxx	x.xxx	x.xxx	0.xxx	xx.xxx		
Placebo	3	xx.xx	0.xxx	0.xxx	0.xxx						
ASP8062	4	xx.xx	0.xxx	0.xxx	0.xxx	x.xxx	x.xxx	0.xxx	xx.xxx		
Placebo	4	xx.xx	0.xxx	0.xxx	0.xxx						
ASP8062	5	xx.xx	0.xxx	0.xxx	0.xxx	x.xxx	x.xxx	0.xxx	xx.xxx		
Placebo	5	xx.xx	0.xxx	0.xxx	0.xxx						
ASP8062	6	xx.xx	0.xxx	0.xxx	0.xxx	x.xxx	x.xxx	0.xxx	xx.xxx		
Placebo	6	xx.xx	0.xxx	0.xxx	0.xxx						
ASP8062	Overall	xx.xx	0.xxx	0.xxx	0.xxx	x.xxx	x.xxx	0.xxx	xx.xxx		
Placebo	Overall	xx.xx	0.xxx	0.xxx	0.xxx						

 SE is standard error;  CI is confidence interval

*Programming note: If a transformation of the dependent variable is used add 2 columns: p-value and Cohen's d for the transformed model.*

Table 45 is the template for Tables 76, 78, 80, 82, 84, and 86. Table 75 is the template for Tables 77, 79, 81, 83, 85, and 87.

**Table 76: Percentage of Heavy Drinking Days per Week (mITT) – Weeks 3-6**

**Table 77: Percentage of Heavy Drinking Days per Week (mITT) – Full Model, Mixed Effects, Weeks 3-6**

**Table 78: Percentage of Very Heavy Drinking Days per Week (mITT) – Weeks 3-6**

**Table 79: Percentage of Very Heavy Drinking Days per Week (mITT) – Full Model, Mixed Effects, Weeks 3-6**

**Table 80: Drinks per Week (mITT) – Weeks 3-6**

**Table 81: Drinks per Week (mITT) – Full Model, Mixed Effects, Weeks 3-6**

**Table 82: Drinks per Drinking Day (mITT) – Weeks 3-6**

**Table 83: Drinks per Drinking Day (mITT) – Full Model, Mixed Effects, Weeks 3-6**

**Table 84: Mean Cigarettes Smoked Among Smokers (mITT) – Weeks 3-6**

**Table 85: Mean Cigarettes Smoked Among Smokers (mITT) – Full Model, Mixed Effects, Weeks 3-6**

**Table 86: PACS (mITT) – Weeks 3-6**

**Table 87: PACS (mITT) – Full Model, Mixed Effects, Weeks 3-6**

**Table 88: Percentage of Subjects Abstinent from Nicotine Use Weeks 3-6 – Among Subjects that Used Nicotine Products at Baseline**

	ASP8062	Placebo	Total
	(N=xx)	(N=xx)	(N=xxx)
No Nicotine Use			
Yes	xx (xx.x%)	xx (xx.x%)	xx (xx.x%)
No	xx (xx.x%)	xx (xx.x%)	xx (xx.x%)

 Nicotine use includes cigarettes or other nicotine products

**Table 89: Percentage of Subjects Abstinent from Nicotine Use Weeks 3-6 – Full Model Logistic Regression (Among Nicotine Users at Baseline)**

									95% CI 	
Parameter		DF 	Estimate	Standard Error	Wald Chi-Square	Pr > Chi-Square	Cohen's h	OR 	Upper CI	Lower CI
Intercept		1	xx.XXX	xx.XXX	xx.XXX	0.XXX				
Treatment	Overall	x	xx.XXX	xx.XXX	xx.XXX	0.XXX				

									95% CI 	
Parameter		DF 	Estimate	Standard Error	Wald Chi-Square	Pr > Chi-Square	Cohen's h	OR 	Upper CI	Lower CI
Treatment 	ASP8062	x	xx.xxx	xx.xxx	xx.xxx	0.xxx	0.xxx	xx.xxx	xx.xxx	xx.xxx
Site	Overall	x	xx.xxx	xx.xxx	xx.xxx	0.xxx				
Site 	1	x	xx.xxx	xx.xxx	xx.xxx	0.xxx		xx.xxx	xx.xxx	xx.xxx
Site	2	x	xx.xxx	xx.xxx	xx.xxx	0.xxx		xx.xxx	xx.xxx	xx.xxx
Cov		x	xx.xxx	xx.xxx	xx.xxx	0.xxx		xx.xxx	xx.xxx	xx.xxx

 Nicotine use includes either cigarettes or other nicotine products;  DF is degrees of freedom;  OR is odds ratio;  CI is confidence interval;  Comparison to placebo for each active treatment;  Site 3 is reference for the OR

*Programming note: COV is baseline equivalent of dependent variable and any other covariate(s) which have not been specified at the time of writing of SAP*

**Table 90: Percentage of Subjects Abstinent from Smoking Weeks 3-6 – Among Baseline Smokers**

Same analysis as Table 88

**Table 91: Percentage of Subjects Abstinent from Smoking Weeks 3-6 – Full Model Logistic Regression (Among Baseline Smokers)**

Same analysis as Table 89

**Table 92: PSQI Scores – mITT Subjects**

		ASP8062				Placebo			
Study Week	N	Mean (SD  )	Median	(Min-Max)	N	Mean (SD)	Median	(Min-Max)	
1	xx	xxx (xx)	xxx	(xx-xx)	xx	xxx (xx)	xxx	(xx-xx)	
5	xx	xxx (xx)	xxx	(xx-xx)	xx	xxx (xx)	xxx	(xx-xx)	
7	xx	xxx (xx)	xxx	(xx-xx)	xx	xxx (xx)	xxx	(xx-xx)	

 SD is standard deviation

**Table 93: PSQI Scores (mITT) – Full Model, Mixed Effects, Weeks 5 & 7****Type III Wald Tests**

Parameter	Num DF 	Den DF 	F Value	p-value
Arm	1	xx	xxx.xx	0.xxx
Site	xx	xx	xxx.xx	0.xxx
Baseline PSQI	1	xx	xxx.xx	0.xxx

 Numerator degrees of freedom;  Denominator degrees of freedom

**Least Squares Means**

				95% CI 				Model	
Arm	Week	Estimate	SE 	Lower CI	Upper CI	Difference	SE	p-value	Cohen's d
ASP8062	5	xx.xx	0.xxx	0.xxx	0.xxx	x.xxx	x.xxx	0.xxx	xx.xxx
Placebo	5	xx.xx	0.xxx	0.xxx	0.xxx				
ASP8062	7	xx.xx	0.xxx	0.xxx	0.xxx	x.xxx	x.xxx	0.xxx	xx.xxx
Placebo	7	xx.xx	0.xxx	0.xxx	0.xxx				

 SE is standard error;  CI is confidence interval

*Programming note: If a transformation of the dependent variable is used add 2 columns: p-value and Cohen's d for the transformed model.*

**Table 94: POMS Total Mood Disturbance Score – mITT**

Study Week	ASP8062				Placebo			
	N	Mean (SD  )	Median	(Min-Max)	N	Mean (SD)	Median	(Min-Max)
1	xx	xxx (xx)	xxx	(xx-xx)	xx	xxx (xx)	xxx	(xx-xx)
5	xx	xxx (xx)	xxx	(xx-xx)	xx	xxx (xx)	xxx	(xx-xx)
7	xx	xxx (xx)	xxx	(xx-xx)	xx	xxx (xx)	xxx	(xx-xx)

 SD is standard deviation

**Table 95: POMS Total Mood Disturbance Score (mITT) – Full Model, Mixed Effects, Weeks 5 & 7**

**Type III Wald Tests**

Parameter	Num DF 	Den DF 	F Value	p-value

Parameter	Num DF 	Den DF 	F Value	p-value
Arm	1	xxx	xxx.xx	0.xxx
Week	1	xxx	xxx.xx	0.xxx
Site	2	xxx	xxx.xx	0.xxx
Cov	x	xxx	xxx.xx	0.xxx
Arm*Week	x	xxx	xxx.xx	0.xxx

 Numerator degrees of freedom;  Denominator degrees of freedom

*Programming note: Cov is the baseline equivalent of the dependent variable and any additional covariates included in the model.*

### Least Squares Means

				95% CI 				Model	
Arm	Week	Estimate	SE 	Lower CI	Upper CI	Difference	SE	p-value	Cohen's d
ASP8062	4	xx.xx	0.xxx	0.xxx	0.xxx	x.xxx	x.xxx	0.xxx	xx.xxx
Placebo	4	xx.xx	0.xxx	0.xxx	0.xxx				
ASP8062	6	xx.xx	0.xxx	0.xxx	0.xxx	x.xxx	x.xxx	0.xxx	xx.xxx
Placebo	6	xx.xx	0.xxx	0.xxx	0.xxx				
ASP8062	Overall	xx.xx	0.xxx	0.xxx	0.xxx	x.xxx	x.xxx	0.xxx	xx.xxx
Placebo	Overall	xx.xx	0.xxx	0.xxx	0.xxx				

 SE is standard error;  CI is confidence interval

*Programming note: If a transformation of the dependent variable is used add 2 columns: p-value and Cohen's d for the transformed model.*

Table 94 is the template for Tables 96, 98, 100, 102, 104, and 106. Table 95 is the template for Tables 97, 99, 101, 103, 105, and 107

**Table 96: POMS Tension-Anxiety Score – mITT Subjects**

**Table 97: POMS Tension-Anxiety Score (mITT) – Full Model, Mixed Effects, Weeks 5 & 7**

**Table 98: POMS Anger-Hostility Score – mITT Subjects**

**Table 99: POMS Anger-Hostility Score (mITT) – Full Model, Mixed Effects, Weeks 5 & 7**

**Table 100: POMS Vigor-Activity Score – mITT Subjects**

**Table 101: POMS Vigor-Activity Score (mITT) – Full Model, Mixed Effects, Weeks 5 & 7**

**Table 102: POMS Fatigue-Inertia Score – mITT Subjects**

**Table 103: POMS Fatigue-Inertia Score (mITT) – Full Model, Mixed Effects, Weeks 5 & 7**

**Table 104: POMS Confusion-Bewilderment Score – mITT Subjects**

**Table 105: POMS Confusion-Bewilderment Score (mITT) – Full Model, Mixed Effects, Weeks 5 & 7**

**Table 106: POMS Depression-Dejection Score – mITT Subjects**

**Table 107: POMS Depression-Dejection Score (mITT) – Full Model, Mixed Effects, Weeks 5 & 7**

**Table 108: PROMIS Negative Consequences of Alcohol Scores – mITT Subjects**

Study Week	Placebo				N	ANS-6637 200mg		
	N	Mean (SD  )	Median	(Min-Max)		Mean (SD)	Median	(Min-Max)

1	xx	xxx (xx)	xxx	(xx-xx)	xx	xxx (xx)	xxx	(xx-xx)
7	xx	xxx (xx)	xxx	(xx-xx)	xx	xxx (xx)	xxx	(xx-xx)

 SD is standard deviation

**Table 109: ANCOVA PROMIS Negative Consequences of Alcohol – mITT Subjects**

**Type III Wald Test**

Parameter	Num DF 	Den DF 	F Value	p-value
Arm	1	xx	xxx.xx	0.xxx
Site	2	xx	xxx.xx	0.xxx
Baseline PROMIS	1	xx	xxx.xx	0.xxx

 Numerator degrees of freedom;  Denominator degrees of freedom

**Least Squares Means**

Arm	Week	Estimate	SE 	95% CI 		Difference	SE	Model	
				Lower CI	Upper CI			p-value	Cohen's d

Arm	Week	Estimate	SE 	95% CI 		Difference	SE	Model	
				Lower CI	Upper CI			p-value	Cohen's d
ASP8062	7	xx.xx	0.xxx	0.xxx	0.xxx	x.xxx	x.xxx	0.xxx	xx.xxx
Placebo	7	xx.xx	0.xxx	0.xxx	0.xxx				

 SE is standard error;  CI is confidence interval

*Programming note: If a transformation of the dependent variable is used add 2 columns: p-value and Cohen's d for the transformed model.*

### **12.1.6. Safety Analyses**

**Table 110: Overall Summary of Adverse Events – Safety Subjects**

	ASP8062 (N=xx)	Placebo (N=xx)	Total (N=xxx)	p-value
Number of AEs	xx	xx	xx	
Number of SAEs	xx	xx	xx	
Number (%) of subjects with at least one AE	xx (xx.x%)	xx (xx.x%)	xx (xx.x%)	0.xxx
Number (%) of subjects with at least one SAE	xx (xx.x%)	xx (xx.x%)	xx (xx.x%)	0.xxx
Number (%) of subjects with at least one AE related  to study product	xx (xx.x%)	xx (xx.x%)	xx (xx.x%)	0.xxx
Number of AEs by severity				
Mild	xx	xx	xx	
Moderate	xx	xx	xx	
Severe	xx	xx	xx	
Life-threatening	xx	xx	xx	
Number of AEs by relationship to study product				
At least possibly related	xx	xx	xx	
Unrelated	xx	xx	xx	
Number of AEs by SAE status				
No	xx	xx	xx	
Yes	xx	xx	xx	

p-value from chi-square test  Related is possible, probable, or definite

**Table 111: Number and Percentage of Subjects with Adverse Events - Safety Subjects**

MedDRA System Organ Class/	ASP8062	Placebo
Preferred Term	(N=xx)	(N=xx)
- Any Adverse Events -	xx (xx.x%)	xx (xx.x%)
SOC		
- Overall -	xx (xx.x%)	xx (xx.x%)
Preferred term 1	xx (xx.x%)	xx (xx.x%)
Preferred term 2	xx (xx.x%)	xx (xx.x%)

Notes: Percentages are based on the total number of subjects, as given in the column heading.

Multiple occurrences of a specific adverse event for a subject are counted once in the frequency for the adverse event. Likewise, multiple occurrences of adverse events within a specific preferred term for a subject are counted once in the frequency for the preferred term.

*Programmer's Notes: Order System Organ Class alphabetically and preferred term alphabetically within System Organ Class.*

**Table 112: Summary of Subjects with Adverse Events by Severity and Relationship – ASP8062**

Number of Subjects (%) (N=x)												
SOC	MedDRA PT	Mild		Moderate		Severe		Life-threatening		All Grades		
		R	NR	R	NR	R	NR	R	NR	R	NR	R + NR
		xx (xx.x%)	xx (xx.x%)	xx (xx.x%)	xx (xx.x%)	xx (xx.x%)						

Notes: Events are counted once per subject at the highest severity grade and closest relationship to the investigational product. R= related to investigational product (possibly, probably, definitely). NR = not related to investigational product (unrelated, unlikely).

**Table 113: Summary of Subjects with Adverse Events by Severity and Relationship – Placebo**

Number of Subjects (%) (N=x)												
SOC	MedDRA PT	Mild		Moderate		Severe		Life-threatening		All Grades		
		R	NR	R	NR	R	NR	R	NR	R	NR	R + NR
		xx (xx.x%)	xx (xx.x%)	xx (xx.x%)	xx (xx.x%)	xx (xx.x%)						

Notes: Events are counted once per subject at the highest severity grade and closest relationship to the investigational product. R= related to investigational product (possibly, probably, definitely). NR = not related to investigational product (unrelated, unlikely).

**Table 114: Number and Percentage of Subjects with Adverse Events by Maximum Severity - Safety Subjects**

MedDRA SOC/ Preferred Term	ASP8062 (N=xx)				Placebo (N=xx)			
	Mild	Moderate	Severe	Life-threatening	Mild	Moderate	Severe	Life-threatening
- Any Adverse Events -	nn (xx.x%)	nn (xx.x%)	nn (xx.x%)	nn (xx.x%)	nn (xx.x%)	nn (xx.x%)	nn (xx.x%)	nn (xx.x%)
SOC								
- Overall -	nn (xx.x%)	nn (xx.x%)	nn (xx.x%)	nn (xx.x%)	nn (xx.x%)	nn (xx.x%)	nn (xx.x%)	nn (xx.x%)
Preferred term 1	nn (xx.x%)	nn (xx.x%)	nn (xx.x%)	nn (xx.x%)	nn (xx.x%)	nn (xx.x%)	nn (xx.x%)	nn (xx.x%)
Preferred term 2	nn (xx.x%)	nn (xx.x%)	nn (xx.x%)	nn (xx.x%)	nn (xx.x%)	nn (xx.x%)	nn (xx.x%)	nn (xx.x%)

Notes: Percentages are based on the total number of subjects, as given in the column heading.

Multiple occurrences of a specific adverse event for a subject are counted once in the frequency for the adverse event. Likewise, multiple occurrences of adverse events within a specific preferred term for a subject are counted once in the frequency for the preferred term.

*Programmer's Notes: Order System Organ Class alphabetically and preferred term alphabetically within System Organ Class.*

**Table 115: Number and Percentage of Subjects Adverse Events by Relatedness - Safety Subjects**

MedDRA SOC/ Preferred Term	ASP8062		Placebo	
	Related	Not-Related	Related	Not-Related
SOC	nn (xx.x%)	nn (xx.x%)	nn (xx.x%)	nn (xx.x%)
- Overall -				
Preferred term 1	nn (xx.x%)	nn (xx.x%)	nn (xx.x%)	nn (xx.x%)
Preferred term 2	nn (xx.x%)	nn (xx.x%)	nn (xx.x%)	nn (xx.x%)

Related are possibly, probably or definitely related to investigational product

 Not Related to investigational product (not related or unlikely)

**Table 116: Number and Percentage of Subjects with Treatment-Related Adverse Events by Maximum Severity- Safety Subjects**

MedDRA SOC/ Preferred Term	ASP8062 (N=xx)				Placebo (N=xx)			
	Mild	Moderate	Severe	Life-threatening	Mild	Moderate	Severe	Life-threatening
	SOC	nn (xx.x%)	nn (xx.x%)	nn (xx.x%)	nn (xx.x%)	nn (xx.x%)	nn (xx.x%)	nn (xx.x%)
- Overall -								
Preferred term 1	nn (xx.x%)	nn (xx.x%)	nn (xx.x%)	nn (xx.x%)	nn (xx.x%)	nn (xx.x%)	nn (xx.x%)	nn (xx.x%)
Preferred term 2	nn (xx.x%)	nn (xx.x%)	nn (xx.x%)	nn (xx.x%)	nn (xx.x%)	nn (xx.x%)	nn (xx.x%)	nn (xx.x%)

Notes: Percentages are based on the total number of subjects, as given in the column heading.

Multiple occurrences of a specific adverse event for a subject are counted once in the frequency for the adverse event. Likewise, multiple occurrences of adverse events within a specific preferred term for a subject are counted once in the frequency for the preferred term.

*Programmer's Notes: Order System Organ Class alphabetically and preferred term alphabetically within System Organ Class.*

**Table 117: Number and Percentage of Subjects with Adverse Events Occurring in >= 5% of Subjects in Any One Group - Safety Subjects**

MedDRA SOC/ Preferred Term	ASP806 (N=xx)	Placebo (N=xx)	p-value 
SOC	nn (xx.x%)	nn (xx.x%)	x.XXX
- Overall -			
Preferred term 1	nn (xx.x%)	nn (xx.x%)	x.XXX
Preferred term 2	nn (xx.x%)	nn (xx.x%)	x.XXX

Notes: Percentages are based on the total number of subjects, as given in the column heading.

Multiple occurrences of a specific adverse event for a subject are counted once in the frequency for the adverse event. Likewise, multiple occurrences of adverse events within a specific preferred term for a subject are counted once in the frequency for the preferred term. At least % occurring in either arm to be included in the table.

p-value from Fisher's exact test

*Programmer's Notes: Order System Organ Class alphabetically and preferred term alphabetically within System Organ Class.*

**Table 118: Number and Percentage of Subjects with Adverse Events Leading to Discontinuation of Study - Safety Subjects**

MedDRA SOC/ Preferred Term	ASP8062 (N=xx)	Placebo (N=xx)
SOC		
- Overall -	nn (xx.x%)	nn (xx.x%)
Preferred term 1	nn (xx.x%)	nn (xx.x%)
Preferred term 2	nn (xx.x%)	nn (xx.x%)

Notes: Percentages are based on the total number of subjects, as given in the column heading.

Multiple occurrences of a specific adverse event for a subject are counted once in the frequency for the adverse event. Likewise, multiple occurrences of adverse events within a specific preferred term for a subject are counted once in the frequency for the preferred term.

*Programmer's Notes: Order System Organ Class alphabetically and preferred term alphabetically within System Organ Class.*

**Table 119: Number and Percentage of Subjects with Adverse Events Leading to Discontinuation of Study Drug – Safety Subjects**

MedDRA SOC/ Preferred Term	ASP8062 (N=xx)	Placebo (N=xx)
SOC		
- Overall -	nn (xx.x%)	nn (xx.x%)
Preferred term 1	nn (xx.x%)	nn (xx.x%)
Preferred term 2	nn (xx.x%)	nn (xx.x%)

Notes: Percentages are based on the total number of subjects, as given in the column heading.

Multiple occurrences of a specific adverse event for a subject are counted once in the frequency for the adverse event. Likewise, multiple occurrences of adverse events within a specific preferred term for a subject are counted once in the frequency for the preferred term.

*Programmer's Notes: Order System Organ Class alphabetically and preferred term alphabetically within System Organ Class.*

**Table 120: CIWA-AR Score  $\geq 10$  at Least Once During Treatment – Safety Subjects**

	ASP8062	Placebo				95% CI 	
	(N=xx)	(N=xx)	p-value 	Cohen's h	Odds Ratio	OR  Lower CI	OR Upper CI
CIWA-AR Score <math>\geq 10</math>							
Never	xx (xx.x%)	xx (xx.x%)					
At Least Once	xx (xx.x%)	xx (xx.x%)	0.xxx				
ASP8062 vs Placebo				0.xx	xx.XXX	xx.XXX	xx.XXX

 Chi-squared test;  CI is confidence interval;  OR is odds ratio

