
Number of Subjects (Planned): 60
Main Inclusion/Exclusion Criteria: Subjects will be male and female at least 21 years of age with 4 or more DSM-5™ symptoms of AUD (moderate to severe AUD). They must also be seeking treatment for AUD and if male, report drinking an average of at least 28 drinks per week or if female report drinking an average of at least 21 drinks per week prior to consent, and have at least 1 heavy drinking day (4 or more drinks per day for women/5 or more drinks per day for men) during the 7-day period prior to randomization.
Investigational Product, Dosage and Mode of Administration: The target doses are 25 mg tablet of ASP8062 by oral administration once daily at bedtime for 6 weeks.
Reference Therapy, Dosage and Mode of Administration: Subjects in the placebo group will take an equivalent number of identically matched placebo tablets (one per day) by oral administration once daily at bedtime for 6 weeks.
Duration of Study: Each subject will participate in the study for up to 11 weeks, including up to 2 weeks of screening, 6 weeks of treatment, one end-of-study visit during the week following the last treatment dose, and a final telephone contact ~2 weeks after completing treatment for a safety follow-up.

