Criteria for Evaluation: Primary: The primary efficacy endpoint is the “strength” of alcohol craving Visual Analog Scale (VAS) score (item 1 below) upon presentation of the alcohol during the cue session at Week 3 – after two weeks of investigational product treatment. Confirmatory secondary endpoints include the VAS scores for the other 3 VAS scales (items 2 through 4 below) and the average score of the 4 VAS craving items; and the difference score (alcohol cue VAS score minus water cue VAS score) for all 4 of the individual VAS craving items and their average score. The beverage liking VAS item is also a confirmatory secondary endpoint. The 4 VAS craving items in order of appearance are: 
1. How strong is your craving to drink alcohol? - note this is the primary efficacy endpoint2. Having a drink would make things just perfect.3. If I could drink alcohol now, I would drink it.4. It would be hard to turn down a drink right now. The beverage liking item is: How much did you like the beverage just shown to you? Secondary: Secondary efficacy endpoints will be analyzed over the last 4 weeks of the treatment period. 
1. Percentage of subjects with no heavy drinking days. A “heavy drinking day” is 4 or more drinks per drinking day for women and 5 or more drinks per drinking day for men.2. Percentage of subjects abstinent from alcohol.3. Percentage of subjects with at least a World Health Organization (WHO) 2-level decrease in alcohol consumption.4. Percentage of subjects with at least a WHO 1-level decrease in alcohol consumption.5. Percentage of days abstinent per week.6. Percentage of heavy drinking days per week.7. Percentage of very heavy drinking days per week. A “very heavy drinking day” is 8 or more drinks per drinking day for women and 10 or more drinks per drinking day for men.8. Weekly mean number of drinks per week.9. Weekly mean drinks per drinking day.10. Cigarettes smoked per week among smokers.11. Percentage of subjects with no nicotine use among those reporting nicotine use at baseline.12. Alcohol craving score (PACS).13. Sleep quality (PSQI) score (and subscale scores).14. Profile of Mood States (POMS) score (and subscale scores).15. PROMIS Alcohol Negative Consequences score. Safety Endpoints: Safety endpoints will be analyzed over the entire treatment and follow-up period. 
1. Vital signs

2. Body weight
3. Clinical laboratory parameters

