**Table 1: Schedule of Assessments**

Study Phase	Screening	Treatment					End of Study a	Follow-up Call
Clinic Visit #	1	2	3	4	5	6	7	
Study Week (Days) b	-2 to -1 (-14 to -1)	1 (1 to 7)	2 (8 to 14)	3 (15 to 21)	4 (22 to 28)	5 (29 to 35)	7 (43 to 49)	9 (57 to 63)
Informed Consent	X							
Alcohol Breathalyzer	X	X	X	X	X	X	X	
Urine Drug Test c	X	X	X	X	X	X	X	
Locator Form	X	Update	Update	Update	Update	Update	Update	
Demographics	X							
Medical History	X	Update						
Physical Exam	X	Update						
Body Weight	X				X		X	
MINI	X							
C-SSRS		X	X	X	X	X	X	
Clinical Chemistry d	X				X		X	
Hematology e	X				X		X	
Medical Urinalysis f	X				X		X	
Pregnancy Test	X	X					X	
Birth control methods (all subjects)	X	Update	Update	Update	Update	Update	Update	

Study Phase	Screening	Treatment					End of Study a	Follow-up Call
Clinic Visit #	1	2	3	4	5	6	7	
Study Week (Days) b	-2 to -1 (-14 to -1)	1 (1 to 7)	2 (8 to 14)	3 (15 to 21)	4 (22 to 28)	5 (29 to 35)	7 (43 to 49)	9 (57 to 63)
Vital Signs g	X	X	X	X	X	X	X	
Eligibility Checklist	X	X						
Drinking Goal	X							
ECG	X				X		X	
Prior and Concomitant Meds	X	X	X	X	X	X	X	X
CIWA-AR	X	X	X	X	X	X	X	X
Screening Cue Reactivity Session: VAS Scales	X							
Randomization		X (Day 1)						
Blood for Drug Concentration					X		X	
Drug compliance/ accountability/ Review AiCure		Dispense Day 1	X	X	X	X	X	
AEs (open ended question)		X	X	X	X	X	X	X
Brief Telephone Interview h		once during the week	once during the week	As needed if the subject misses a clinic visit				
Take Control		X	X	X	X i	X	X	
Treatment Cue Reactivity Session: VAS Scales				X				

Study Phase	Screening	Treatment					End of Study a	Follow-up Call
Clinic Visit #	1	2	3	4	5	6	7	
Study Week (Days) b	-2 to -1 (-14 to -1)	1 (1 to 7)	2 (8 to 14)	3 (15 to 21)	4 (22 to 28)	5 (29 to 35)	7 (43 to 49)	9 (57 to 63)
TLFB	X	X	X	X	X	X	X	
Brief Drinking Questionnaire	as needed							
Exit Interview							X	
ACQ-SF-R	2X pre/post cue session			2X pre/post cue session				
PACS		X	X	X	X	X	X	
Cigarette smoking quantity/frequency and nicotine use		X				X	X	
PSQI		X				X	X	
POMS		X				X	X	
PROMIS Alcohol Negative Consequences		X					X	
Hyperkatifeia Scale		X						
Treatment Referral							X	
Follow-Up Telephone Interview								X
Final Subject Disposition								X

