a EOS - end of study. These assessments are to be done at Week 7 or if the subject discontinues early and agrees to a final clinic visit.

b Within each study week, there should be a least two days elapsed since the visit in the prior week.

- c Test for opiates (i.e., morphine test), cocaine, amphetamines, methamphetamine, THC, buprenorphine, methadone, benzodiazepines, oxycodone, barbiturates, 3,4-methylenedioxy-methamphetamine (MDMA – also known as ecstasy), and EtG.
- d Creatinine, urea nitrogen, total bilirubin, ALT, AST, alkaline phosphatase, GGT, albumin, total cholesterol, triglycerides, sodium, potassium, and chloride
- e Complete blood cell count including RBC, WBC, hemoglobin, hematocrit, and platelets.
- f A dipstick urinalysis will be performed that tests for specific gravity, ketones, pH, protein, blood, glucose, nitrites, bilirubin, and leukocyte esterase. If the dipstick is positive for blood, leukocyte esterase, or protein, then a microscopic analysis will be performed at the discretion of the investigator.
- g Sitting blood pressure and heart rate.
- h Telephone calls after the Week 1 and 2 in clinic visits will collect AEs, concomitant medications, CIWA-AR, and give a drug compliance reminder. The call during Week 2 should be several days before the cue session to remind the subject of the planned visit.
- i Two modules will be viewed this week.

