#### **9.6.4. CIWA-AR Scores**

The number and percentage of subjects who reported CIWA-AR scores  $\geq 10$  at any time after the start of dosing will be presented.

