**Table 2: Exposure to Investigational Products Using AICure Data – mITT Subjects**

	Number of Tablets Taken								
	ASP8062 N=XX				Placebo N=XX				
	N	Mean (SD  )	Med	(Min-Max)	N	Mean (SD)	Med	(Min-Max)	p-value 
Week 1	xx	xx.x (xx.x)	xx.x	(xx.x-xx.x)	xx	xx.x (xx.x)	xx.x	(xx.x-xx.x)	0.xxx
Week 2	xx	xx.x (xx.x)	xx.x	(xx.x-xx.x)	xx	xx.x (xx.x)	xx.x	(xx.x-xx.x)	0.xxx
Week 3	xx	xx.x (xx.x)	xx.x	(xx.x-xx.x)	xx	xx.x (xx.x)	xx.x	(xx.x-xx.x)	0.xxx
Week 4	xx	xx.x (xx.x)	xx.x	(xx.x-xx.x)	xx	xx.x (xx.x)	xx.x	(xx.x-xx.x)	0.xxx
Week 5	xx	xx.x (xx.x)	xx.x	(xx.x-xx.x)	xx	xx.x (xx.x)	xx.x	(xx.x-xx.x)	0.xxx
Week 6	xx	xx.x (xx.x)	xx.x	(xx.x-xx.x)	xx	xx.x (xx.x)	xx.x	(xx.x-xx.x)	0.xxx
Total Dose 	xx	xx.x (xx.x)	xx.x	(xx.x-xx.x)	xx	xx.x (xx.x)	xx.x	(xx.x-xx.x)	0.xxx

 p-value from t-test Dose is the total number of tablets taken, maximum prescribed is 42 tablets SD is standard deviation**Table 3: Total Exposure to Investigational Products Using AICure Data – Evaluable Subjects**

Same as Table 2 only using evaluable subjects

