**Table 30: Baseline Alcohol-Related Craving, Consequences, Withdrawal and Hyperkatifeia – mITT Subjects**

	ASP8062	Placebo	Total	
Parameter	(N=xx)	(N=xx)	(N=xxx)	p-value
Pre-cue ACQ-SF-R^2				0.xxx
Mean	xx.x	xx.x	xx.x	
SD 	xx.x	xx.x	xx.x	
Median	xx.x	xx.x	xx.x	
Min-Max	(xx-xx)	(xx-xx)	(xx-xx)	
Scale Min-Max			(xx.x – xx.x)	
Post-cue ACQ-SF-R				0.xxx
Mean	xx.x	xx.x	xx.x	
SD	xx.x	xx.x	xx.x	
Median	xx.x	xx.x	xx.x	
Min-Max	(xx-xx)	(xx-xx)	(xx-xx)	
Pre-Post ACQ-SF-R				
Mean	xx.x	xx.x	xx.x	
SD	xx.x	xx.x	xx.x	
Median	xx.x	xx.x	xx.x	
Min-Max	(xx-xx)	(xx-xx)	(xx-xx)	
PROMIS Alcohol Negative Consequences (T-scores)				0.xxx
Mean	xx.x	xx.x	xx.x	
SD	xx.x	xx.x	xx.x	
Median	xx.x	xx.x	xx.x	
Min-Max	(xx-xx)	(xx-xx)	(xx-xx)	
PACS				0.xxx
Mean	xx.x	xx.x	xx.x	
SD	xx.x	xx.x	xx.x	
Median	xx.x	xx.x	xx.x	
Min-Max	(xx-xx)	(xx-xx)	(xx-xx)	
Scale Min-Max			(xx.x – xx.x)	
CIWA-AR^6				0.xxx
Mean	xx.x	xx.x	xx.x	
SD	xx.x	xx.x	xx.x	
Median	xx.x	xx.x	xx.x	
Min-Max	(xx-xx)	(xx-xx)	(xx-xx)	
Scale Min-Max			(xx.x – xx.x)	

	ASP8062	Placebo	Total	
Parameter	(N=xx)	(N=xx)	(N=xxx)	p-value
Withdrawal Symptoms (CIWA <math>\geq</math> 10)	xx (xx.x%)	xx (xx.x%)	xx (xx.x%)	0.xxx
Hyperkatifeia				0.xxx
Mean	xx.x	xx.x	xx.x	
SD	xx.x	xx.x	xx.x	
Median	xx.x	xx.x	xx.x	
Min-Max	(xx-xx)	(xx-xx)	(xx-xx)	
Scale Min-Max			(xx.x – xx.x)	
Stress Anxiety				0.xxx
Mean	xx.x	xx.x	xx.x	
SD	xx.x	xx.x	xx.x	
Median	xx.x	xx.x	xx.x	
Min-Max	(xx-xx)	(xx-xx)	(xx-xx)	
Scale Min-Max			(xx.x – xx.x)	
Depression				0.xxx
Mean	xx.x	xx.x	xx.x	
SD	xx.x	xx.x	xx.x	
Median	xx.x	xx.x	xx.x	
Min-Max	(xx-xx)	(xx-xx)	(xx-xx)	
Scale Min-Max			(xx.x – xx.x)	
Irritable				0.xxx
Mean	xx.x	xx.x	xx.x	
SD	xx.x	xx.x	xx.x	
Median	xx.x	xx.x	xx.x	
Min-Max	(xx-xx)	(xx-xx)	(xx-xx)	
Scale Min-Max			(xx.x – xx.x)	
Pain				0.xxx
Mean	xx.x	xx.x	xx.x	
SD	xx.x	xx.x	xx.x	
Median	xx.x	xx.x	xx.x	
Min-Max	(xx-xx)	(xx-xx)	(xx-xx)	
Scale Min-Max			(xx.x – xx.x)	

 t-test for continuous variables and chi-square test for categorical

ACQ-SF-R is Alcohol Craving Questionnaire – Short Form – Revised

 SD is standard deviation

 PROMIS is short form of Patient-reported Outcomes Information System

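### Table 120 limits the CIWA-AR ≥ 10 count to treatment, while SAP 9.6.4 and the protocol set no end date and carry safety endpoints through follow-up

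*SAP*

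**What the plan says.** **The rule.** SAP 9.6.4 (CIWA-AR Scores) reports the subjects with a score of 10 or more "at any time after the start of dosing will be presented". The protocol synopsis has the same rule under Safety Analyses. Neither gives an end date. Under Safety Endpoints, where CIWA-AR is item 8, the synopsis adds: "Safety endpoints will be analyzed over the entire treatment and follow-up period".

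**The shell.** Table 120 in SAP 12.1.6 counts a score of 10 or more "at Least Once During Treatment". It has rows for never and at least once, a p-value, Cohen's h and an odds ratio. No footnote or programmer note says which visits belong to treatment. The List of Tables repeats the window and prints the cut-off as > 10.

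**The assessments.** The Schedule of Assessments (SAP 3.2, Table 1) marks CIWA-AR in all eight columns: "CIWA-AR X X X X X X X X". Its footnote h adds two more scores: "Telephone calls after the Week 1 and 2 in clinic visits will collect AEs, concomitant medications, CIWA-AR". Week 7 sits under End of Study and Week 9 under Follow-up Call, both outside the Treatment columns. The synopsis (Duration of Study) plans "one end-of-study visit during the week following the last treatment dose".

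**Other CIWA outputs.** Tables 30 and 31 give baseline values, including a row for "Withdrawal Symptoms (CIWA" of 10 or more. Listing 17 shows CIWA-AR by week for mITT subjects.

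**The concern.** The rule and its shell use different windows. One is open-ended from first dose; the other carries a label that, on the schedule's own column headings, stops before the last two assessments. A programmer working from the shell and one working from 9.6.4 could each claim to follow the plan and report different numbers for the same safety endpoint.

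The title may well be taken at face value, because Tables 127 and 128 in the same shell set refer to the whole study. Against that background, Table 120's label looks deliberately narrower.

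At stake is whether scores that the protocol schedules, and undertakes to analyse through follow-up, enter the comparison by arm. Listing 17 may show the late values, but it gives no count by arm. It also covers only mITT subjects, who must have a non-missing primary VAS score, so safety-set subjects without that score are absent from it.

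**Working it through.** **1. When planned dosing ends.** The footnote to shell Table 2 states "maximum prescribed is 42 tablets". One tablet a day for six weeks gives 6 × 7 × 1 = 42, so the figure reproduces and the last planned dosing day is Day 42. Week 7 starts on Day 43 and Week 9 on Day 57. Both follow the last planned dose.

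**2. Scheduled CIWA-AR scores after the first dose**, for a subject who follows the full schedule. The Week 1 visit score is taken as pre-dose, because tablets are dispensed on Day 1 and taken at bedtime.

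| Score | From first dose, no end date | Title, Week 7 in treatment | Title, read literally |
|---|---|---|---|
| Week 1 call | yes | yes | yes |
| Week 2 visit | yes | yes | yes |
| Week 2 call | yes | yes | yes |
| Week 3 visit | yes | yes | yes |
| Week 4 visit | yes | yes | yes |
| Week 5 visit | yes | yes | yes |
| Week 7 visit | yes | yes | no |
| Week 9 call | yes | no | no |
| **Total** | **8** | **7** | **6** |

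The literal reading drops 2/8 = 25% of the scheduled scores, and the wider reading drops 1/8 = 12.5%.

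**3. Support for the middle column.** SAP 9.5 restricts the PROMIS analysis to subjects assessed within the treatment period. SAP 9.4.3.2 and the schedule place PROMIS at baseline and Week 7 only, so for that endpoint the treatment period has to include the Week 7 visit. Nothing similar brings in Week 9.

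**4. Illustration of the effect on the count.** The documents give no rate of scores of 10 or more. Assume each scheduled score reaches 10 independently with probability p. The chance of at least one in k scores is 1 − (1 − p)^k.

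| p (assumed) | k = 6 | k = 7 | k = 8 |
|---|---|---|---|
| 0.5% | 3.0% | 3.4% | 3.9% |
| 1% | 5.9% | 6.8% | 7.7% |
| 2% | 11.4% | 13.2% | 14.9% |
| 5% | 26.5% | 30.2% | 33.7% |

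For example, at p = 1% and k = 8: 1 − 0.99^8 = 0.077. Over this range the literal title lowers the proportion by 0.9 to 7.2 percentage points (3.9 − 3.0 and 33.7 − 26.5). Scores within a subject are probably positively correlated, which would shrink the gap. A higher rate late in the study would widen it. The table shows scale and is not a forecast.

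**The case against.** The strongest reply is that the counting rule is already fixed, in both the protocol and SAP 9.6.4, and that nothing in the body of Table 120 restricts visits. The exclusion is inferred from a few words in a title. SAP section 10 requires tables to be reviewed for consistency with the plan, so a careful programmer would include Weeks 7 and 9. Shell titles are loose elsewhere too: SAP 3.3.3 confines suicidal ideation to the treatment period, yet Table 128 covers the whole study.

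Much of this stands. The exclusion is a possible consequence of the title, not a stated instruction. But a consistency review does not settle the matter when the shells are part of the plan and the plan gives two windows.

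It can also be said that Week 7 counts as treatment. SAP 9.4.3 ties Week 7 data to Week 6, and SAP 9.5 supports the same usage for PROMIS. The first of these concerns secondary efficacy endpoints and the second a single efficacy scale, so neither defines the window for a safety table. Still, they make the narrower loss, the Week 9 call alone, a fair reading.

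Finally, the > 10 in the List of Tables is clerical. The protocol, SAP 5.3, SAP 9.6.4, Table 30 and Table 120 itself all use ≥ 10.

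**Conclusion.** The mismatch is real and modest. Table 120 as titled omits one or two of the eight scheduled scores after first dose, depending on whether Week 7 counts as treatment. The Week 9 call is outside on either reading. The counts assume that the Week 1 visit score precedes the first dose and that the subject follows the full schedule. No efficacy, power or alpha figure changes.

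A reader might infer more than the documents support:

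- *That CIWA-AR is reported nowhere else.* Tables 30 and 31 and Listing 17 carry it. Table 120 is the only post-baseline summary table.
- *That every off-drug score is lost.* Shell Table 1 provides for subjects who stop drug but stay in the study. Their scores at visits in Weeks 2 to 5 may be off drug and would be counted on any reading.
- *That the title removes the last week of dosing.* No CIWA-AR is scheduled in Week 6 (Days 36–42). That gap belongs to the schedule, and retitling does not fill it.
- *That the trial would not have looked after dosing ended.* Adverse events are also collected at Weeks 7 and 9, and Listing 17 can show CIWA-AR values by week.
- *That the late scores are there to detect effects of stopping ASP8062.* SAP 5.3 describes CIWA-AR as a measure of alcohol withdrawal and gives it no other purpose.

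**What to change.** Make three wording changes before the table is programmed:

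1. Retitle Table 120 as *CIWA-AR Score ≥ 10 at Any Time After the Start of Dosing*.
2. Add a programmer note that every visit and call after the first dose counts, up to and including the Week 9 call.
3. Give the List of Tables entry the same title and the ≥ 10 cut-off.

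Optionally, add rows that split scores into those up to and those after each subject's own last-dose date, beside the overall count. The plan promises only the single count by arm, so this goes beyond the correction.

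The cost is a title, a note and a contents entry. The optional rows need one date comparison on data already collected. No new assessment is required.
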